### ***Data Collection Methods, Assessments, Interventions and Schedule***

**Study 1 (Aim 1): The implementation of a practice-based social determinants of health screening and referral intervention in two pediatric hematology clinics to field test key study logistics and understand the facilitators and barriers to implementation and accelerate its adoption**

**Study Procedures.** At baseline and every six months throughout the study period, the Boston Medical Center-based team will conduct focus groups with stakeholders (e.g., clinical and administrative staff) at each of the four pediatric hematology clinic sites to better understand the barriers and facilitators to implementation of WE CARE. The site PI at each institution will help us identify staff members. The BMC-based team will provide an information sheet about Aim 1 of the study in advance so that practitioners and staff have time to consider the consent and come to the focus groups ready with questions regarding the consent. Before beginning the focus groups, the study PIs and members of their research team will meet with clinic stakeholders at their staff meetings and provide an overview of the study. We will conduct focus groups with pediatric hematology clinic staff every six months throughout the study period. At baseline, the Boston Medical Center-based team will conduct focus groups (6-8 individuals per group) with key stakeholders identified by the site PI at the two WE CARE pediatric hematology clinics to better understand the barriers and facilitators to implementation. They will include both clinic leadership and individuals known within the clinic to be thought leaders. The composition of these groups may vary at each time point, but the structure, discussion topics, and goals of the later focus groups will be the same as the earlier focus groups. Individuals participating in multiple focus groups will be re-consented at each time point.

Quality improvement methodology will be used to both gather key information and optimize the implementation of WE CARE. We will employ the Model for Improvement's Plan-Do-Study-Act (PDSA) methodology to assess the implementation of WE CARE in an iterative fashion for one year in each clinic. Best practices regarding key elements of the intervention will be continually assessed throughout the QI phase. [name] will initially meet weekly with clinic stakeholders via video conferencing to review the WE CARE process data and identify areas for improvement. We expect, based on our prior experience that we will gradually scale back to monthly meetings. This phase of the study will not involve human subjects.

*Intervention Fidelity Data:* Study staff, as we have previously done, will collect data on the implementation of WE CARE from the electronic health record (EHR). Specifically, to determine whether WE CARE *screeners were given and whether referrals were made at clinic visits*, and to assess for drift during the study period, we will measure the scanned surveys in the EHR for SCA visits. Of note, the WE CARE survey has a referral checkbox that providers mark if a referral is made. Clinical staff will be instructed to check off the box if she/he provides an information sheet from the Family Resource Book

for an unmet need. Every six months, we will randomly select 10 patients who had a visit and review their EHR for distribution of surveys and referrals. This study phase will not involve human subjects.

**Materials.** The research data will include audio-recordings of focus groups. Only study PIs [name], [name] (co-I), and trained study staff at each of the study sites will have access to participants' identifying information. The site PIs and RAs from the two control sites will not have access to the identifiable qualitative data. We will use excel spread sheets to document our descriptive QI and fidelity data (e.g., distribution of WE CARE surveys, unmet needs, referrals); no HIPAA identifiers will be collected.

***Study 2 (Aim 2): Obtaining population-specific empirical estimates of study parameters to plan a future large-scale cluster RCT of WE CARE for children with SCA***

**Study Procedures.** Parents will be asked to complete a baseline and 12-month follow-up questionnaire at their child's medical visit and complete a brief telephone interview 3, 6, and 9 months post-enrollment.

Eligible study participants will be identified by the front desk staff and research staff at each clinic. Prior to each clinic session, the research staff will identify potentially eligible study subjects by reviewing the daily appointment list. We will also ask front desk personnel to assist us in identifying potential subjects, if they are willing, and, in some sites, to assist in handing out informational flyers. If a family is identified as likely to meet eligibility criteria, a member of the study team will approach potentially eligible parents in a private location at the practice, such as an exam room. If the parent is eligible for the study, a study team member will review the study with him/her. Informed consent will be obtained via written consent. The original hard copies of the ICFs will be stored in a locked file in a locked room in the hematology research space at that site. Each clinical site will maintain a tracker linking each patient to a unique subject ID number, which does not contain any combination of information that allows the identification of a subject; this tracker will not be shared outside that clinical site. Participants will be provided with a copy of their signed informed consent form.

Data will be collected from parents primarily from parent-administered surveys at enrollment and at follow-up which will occur one year post-index visit. These surveys will be completed using a study tablet (e.g., iPad) and backed up on to a HIPAA-compliant Boston Medical Center installation of REDCap, which is backed up on the secure, password-protected Boston University Medical Campus server. To complete these surveys, subjects will enter their unique ID number. A brief telephone interview will be conducted 3, 6, and 9 months post-enrollment to ascertain unmet needs, contact and enrollment in community-based resources, and parent report of prescription refills for penicillin or hydroxyurea. A hair cortisol sample will also be collected from the parent at enrollment and 1-year follow-up. Finally, site research staff will collect data from the electronic health record (EHR) on child health outcomes (i.e., adherence to clinic visits, medication adherence, ED visits, hospitalizations, vaso-occlusive episodes, acute chest syndrome, and infections). Data from the EHR will be collected three times (baseline, 6-months post-enrollment, and 12-months post-enrollment).

*\*Research Electronic Data Capture (REDCap) is a research focused, electronic web-based data capture system. REDCap is a data collection tool and allows for storage and management of both surveys and databases. REDCap is a secure storage system and meets HIPAA compliance standards. REDCap software will be used to facilitate parent consents, questionnaires, and forms.*

**Materials.** The research data will include questionnaires completed by parents/caregivers both in-person and via telephone, parent hair cortisol samples, and medical chart review. Only trained project staff at each clinical site will have access to participants' identifying information.

For the hair cortisol samples, we will be following the hair collection protocol developed by [name] from the University of Massachusetts (UMASS). Hair will be cut at the level of the scalp from 2-3 locations and cut to 3cm at the distal end. Hair samples will be placed directly into a plastic vial; each vial will be labeled by an ID number uniquely linked to each study subject (see below). Hair cortisol is stable at room temperature indefinitely, thus vials will be stored in a locked file cabinet.

For the *medical chart review*, existing trained research staff members at each study site, will collect the data. We decided to use existing research staff for the data collection component of the study since getting chart review credentialing is difficult at each of the study sites. At baseline and 12-month follow-up, medical charts will be reviewed in order to determine the number of appointments kept versus cancelled or no-show, the number of days covered by prescription refills for penicillin and hydroxyurea, and blood tests for monitoring hydroxyurea (including WBC, HB F%, and MCV). At 6-month and 12-month follow-up, medical charts will be reviewed in order to determine the frequency of vaso-occlusive episodes, acute chest syndrome, and sepsis diagnoses.

All enrolled parent-child dyad study participants will be assigned ID numbers which do not contain personal identifiers. All data will be tracked using these ID numbers. The data will be stored in computer files that are protected by a series of passwords known only to study staff and will be stored separately from participant identifiers (i.e., child's name, medical record number). Only the PIs and the research staff at each clinical site will have access to subjects' identities. The master code for each site will be stored in computer files on each site's HIPAA compliant server; they will be protected by a series of passwords known only to the research staff. The database will be stored in computer files on the Boston University Medical Campus HIPAA compliant server; it will also be protected by a series of passwords known only to the Boston Medical Center-based research team (hereafter termed core research team).

***Study 3 (Aim 3): Qualitatively assess possible mechanisms linking SDoH interventions to improved health outcomes, such as increasing a parent's ability to manage their child's disease through medication adherence***

**Study Procedures.** The Boston Medical Center-based team will conduct individual in-depth, semi-structured interviews (~60 minutes) with English- and Spanish-speaking parents of children aged  $\leq 12$  years who receive medical care for SCA at the two control sites (i.e., those in which the WE CARE intervention is not implemented). The interviews will be conducted in a designated private area (e.g., exam room) in the outpatient hematology clinic. A research assistant at the two control sites will coordinate recruitment efforts, which will include telling potentially-eligible families about the study and conducting initial eligibility screening. Specifically, eligibility will be determined by study staff. Eligible children's medical charts will be flagged. We will also ask front desk personnel to assist us in identifying potential subjects, if they are willing, and, in some sites, to assist in handing out informational flyers. The flyer will give a brief description of the project. If a family is identified as likely to meet eligibility criteria, a member of the study team will approach the parent about the study during their child's visit (in a private location at the practice, such as an exam room) and explain to them the purpose of the study and the expectations for the participant. Families who are both eligible and interested in

participating will be scheduled for an interview, which will occur in the hematology clinic on the same day as a future routine medical visit to decrease participant burden. If participants are willing to participate and express a desire to consent during this initial encounter, the site RA will obtain written informed consent from participants at this time; however, participants will not be required to consent during this initial encounter, as they will be given the opportunity to consent on the day of their interview. The RA will work with the site PIs to schedule study participants, and the Boston Medical Center-based research team ([name] and a RA trained in qualitative methodology) will conduct interviews at the control sites. A maximum of 3 interviews will be conducted per day, in order to allow the research team to incorporate interim findings into the interview guide. In this way, data collection and analysis will be iterative.

At the time of the interview, if informed consent has not previously been conducted by the site RA, [name] and the Boston Medical Center-based RA will take responsibility for performing informed consent procedures and collecting qualitative data (both of which will occur at the control sites), as well as managing and analyzing qualitative data. Informed consent will be obtained via written consent. The original hard copies of the ICFs will be stored in a locked file in a locked room in the hematology research space at that site. Each clinical site will maintain a tracker linking each patient to a unique subject ID number, which does not contain any combination of information that allows the identification of a subject; this tracker will not be shared outside that clinical site. Participants will be provided with a copy of their signed informed consent form.

Enrollment will continue until saturation is reached (i.e., more interviews will not generate additional information) in primary research questions. Qualitative interviews will examine parents' perceptions of factors that promote or hinder effective management of their child's SCA. [name] team will conduct interviews in pairs, and therefore will always have a member of the research team available for childcare, if necessary.

**Materials.** The research data will include audio-recordings and transcripts of qualitative interviews with parents. Only study PIs ([name]), co-I ([name]), and trained project staff who are deployed to each of the study sites (hereafter termed core research team) will have access to participants' identifying information. The site PIs and RAs from the two control sites will not have access to the identifiable qualitative data. However, the PIs and RAs from the control sites will be responsible for storing informed consent forms securely at their site.

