## Design and Methods

### *Study Design*

#### ***Study 1 (Aim 1): The implementation of a practice-based social determinants of health screening and referral intervention in two pediatric hematology clinics to field test key study logistics and understand the facilitators and barriers to implementation and accelerate its adoption***

Two of our four proposed pediatric hematology clinical sites will be randomized to implement WE CARE as standard of care for SCA patients. At baseline and every six months throughout the study period, the Boston Medical Center-based team (hereafter termed the core research team) will conduct focus

groups with stakeholders (e.g., clinical and administrative staff) at each of the four pediatric hematology clinic sites to better understand the barriers and facilitators to implementation of WE CARE. The site PI at each institution will help us identify staff members. Before beginning each focus group, the Boston Medical Center PIs and members of their research team will meet with clinic stakeholders at their staff meetings and provide an overview of the study. The Boston Medical Center-based team will conduct focus groups with pediatric hematology clinic staff every six months throughout the study period.

***Study 2 (Aim 2): Obtaining population-specific empirical estimates of study parameters to plan a future large-scale cluster RCT of WE CARE for children with SCA***

For this study, we will be conducting a pilot cluster RCT. Two of our four proposed pediatric hematology clinical sites (Boston Children's Hospital, Connecticut Children's Medical Center, Hasbro Children's Hospital (HCH) and Yale-New Haven Children's Hospital) will be randomized to implement WE CARE as standard of care for SCA patients. To assign the sites to either the control or the intervention group, we will first fix the number of sites to each group (i.e. 2 sites per group) and then assign sites to group using the random function for the uniform distribution in SAS 9.4.

***Study 3 (Aim 3): Qualitatively assess possible mechanisms linking SDoH interventions to improved health outcomes, such as increasing a parent's ability to manage their child's disease through medication adherence***

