## Data Management Methods

**Aim 1. Implement WE CARE in the outpatient pediatric hematology setting.** Focus groups with stakeholders from each clinical site will be conducted at baseline to identify perceived facilitators and barriers to implementation. Once WE CARE is implemented in the two experimental sites, we will gather implementation data from stakeholders every six months. Recordings of the focus groups will be audiotaped and transcribed for analysis as word processing text files suitable for manipulation using the qualitative software program, N-VIVO11. The audio-tapes will be transcribed verbatim; each transcript will then be reviewed by a research assistant for accuracy. Recordings will be destroyed after seven years.

**Aim 2. Obtain population-specific empirical estimates of study parameters to plan a pragmatic large-scale cluster RCT.** Data will be collected from parents primarily from parent-administered surveys at enrollment and at follow-up which will occur one year post-index visit. These surveys will be completed in REDCap\* using a study tablet (e.g., iPad). REDCap (Research Electronic Data Capture) is a research focused, electronic web-based data capture system. REDCap is a data collection tool and allows for storage and management of both surveys and databases. REDCap is a secure storage system and meets HIPAA compliance standards. REDCap software will be used to facilitate parent consent, questionnaires, and forms.

A brief telephone interview will be conducted 3, 6, and 9 months post-enrollment to ascertain unmet needs, and contact and enrollment in community-based resources, and parent report of prescription

refills for penicillin or hydroxyurea. A hair cortisol sample will also be collected from the parent at enrollment and 1-year follow-up. Finally, site research staff will collect data from the electronic health record (EHR) on child health outcomes (i.e., adherence to clinic visits, ED visits, hospitalizations, vaso-occlusive episodes, acute chest syndrome, and infections). Data from the EHR will be collected three times (baseline, 6-months post-enrollment, and 12-months post-enrollment). Recordings will be destroyed after seven years.

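### The plan is inconsistent on whether control clinics hold the six-monthly WE CARE focus groups; if they do, control staff discuss the intervention during outcome follow-up

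*Combined protocol and SAP*

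**What the plan says.** The sections describe the Aim 1 focus groups differently.

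- **Study Design, Study 1.** At baseline and then six-monthly, the core team holds focus "groups with stakeholders (e.g., clinical and administrative staff) at each of the four pediatric hematology clinic sites". Ahead of each group, the team "will meet with clinic stakeholders at their staff meetings and provide an overview of the study".
- **Patient Selection, Study 1.** Staff groups run six-monthly with no restriction by arm. An information sheet goes out in advance, and the overview is given before the groups.
- **Data Collection Methods, Study 1, opening.** "At baseline and every six months throughout the study period, the Boston Medical Center-based team will conduct focus groups", and these are "focus groups with stakeholders (e.g., clinical and administrative staff) at each of the four pediatric hematology clinic sites".
- **Data Collection Methods, Study 1, later in the same paragraph.** The baseline groups are held "with key stakeholders identified by the site PI at the two WE CARE pediatric hematology clinics". Participants are to include clinic leaders and recognised opinion leaders. The plan adds that "the structure, discussion topics, and goals of the later focus groups will be the same as the earlier focus groups".
- **Data Management Methods, Aim 1.** "Focus groups with stakeholders from each clinical site will be conducted at baseline to identify perceived facilitators and barriers to implementation". Then: "Once WE CARE is implemented in the two experimental sites, we will gather implementation data from stakeholders every six months".
- **Definition of Primary and Secondary Outcomes.** The topics are the evidence for WE CARE, the context that helps or hinders it, and its facilitation.
- **Statistical Power and Sample Considerations.** Up to 15 staff at each site and 60 in all, within a total of 235 that includes 175 parents. The same section says that control-group estimates will be the basis for powering the future trial.

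**The concern.** There are two problems. The first is operational: a control-site team cannot tell from the protocol whether it holds focus groups at baseline only, every six months, or not at all.

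The second follows if the four-site wording is applied. Staff at clinics randomized to usual care would be brought together during follow-up to discuss an intervention that their clinic does not have. Some of them may be the people best placed to change practice. The discussion could lead them to ask about social needs or hand out referrals more often than they otherwise would. Needs identification and referral provision head the list of Aim 2 primary outcomes, so any such change would fall directly on what is measured in the control arm. The pilot's main quantitative product is a set of control-group estimates for planning a larger trial, and these should describe usual care without prompting by the study.

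**Working it through.** **1. Site scope, section by section**

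- Study Design: four sites at baseline, four sites six-monthly.
- Data Collection Methods, opening: four sites at baseline, four sites six-monthly.
- Data Collection Methods, later sentences: two WE CARE sites at baseline. Later rounds repeat the same structure and goals, so two sites is implied for them too.
- Data Management Methods: each site at baseline. The six-monthly rounds are tied to implementation at the two experimental sites, by implication.

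The baseline round is in direct conflict (four sites against two). For the six-monthly rounds, the four-site text is explicit and the two-site text is implied.

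**2. Staff numbers**

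Inputs from Statistical Power and Sample Considerations: 15 staff per site, 60 staff, 175 parents, 235 in total.

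- Four sites: 15 × 4 = 60, and 60 + 175 = 235. The plan's figures reproduce.
- Two sites only: 15 × 2 = 30, and 30 + 175 = 205. They do not.

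The ceiling therefore assumes that control clinics take part. It does not show how often: groups at all four sites at baseline and at two sites afterwards would also fit 60.

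**3. Timing against outcome follow-up**

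Inputs from Study Timeline, as the table reads:

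- pre-implementation stakeholder data, Year 1 Q2 to Q3;
- Aim 1 assessment, Year 1 Q3 to Year 4 Q3;
- Aim 2 accrual, Year 1 Q4 to Year 2 Q4;
- Aim 2 data collection, Year 1 Q4 to Year 4 Q3.

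Each family is followed for 12 months.

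- Rounds within one family's follow-up: 12 / 6 = 2.
- Rounds at a clinic between first enrolment and the last 12-month visit: accrual ending in Year 2 Q4 plus 12 months reaches about Year 3 Q4. That is 9 quarters, or 27 months, and 27 / 6 = 4.5, so about four rounds.

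The baseline round belongs to the pre-implementation period, before accrual starts. The interim rounds are the ones that fall inside the outcome window.

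**4. Safeguards**

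No section limits what control-clinic staff are told. The fidelity check reads scanned WE CARE surveys in the health record, so it would not pick up informal screening or referral at a control clinic. Parent questionnaires ask whether handouts were given, but cannot separate usual care from care prompted by the study.

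**The case against.** The best defence is that control-site groups are a reasonable design choice. Clinics that have not implemented WE CARE can still report their attitudes to the evidence and their organizational context. The Aim 1 analysis compares sites, and staff turnover is a reason to repeat the groups. This stands. A reader might infer that interim control-site groups have nothing to report, but the plan's own framework does not support that. Only the facilitation topic lacks an object there.

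A reader might also infer that control staff are repeatedly briefed on the intervention. The documents do not establish this. Only Study Design puts the overview before each group. Patient Selection and Data Collection Methods refer to the groups collectively, which is compatible with a single overview. What is described is an overview of the study, not training in WE CARE. The sentences on leaders and on unchanged topics follow the two-clinic sentence, so applying them to control clinics is a possible reading, not a certain one.

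Third, contamination is possible but not shown. The intervention consists of a survey, resource sheets and trained staff, and it is implemented at two of the four sites. Discussion alone is a weaker stimulus. Parents are also telephoned about unmet needs at 3, 6 and 9 months, with no restriction by arm. That is a separate exposure, and changing the focus groups would not remove it. These points limit how large the problem is likely to be. They do not resolve the conflicting text or give a reason to leave an avoidable exposure in place.

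**Conclusion.** The inconsistency is established from the text. The four-site schedule is the dominant reading: it appears in Study Design and Data Collection Methods, and the staff ceiling is consistent with it. The two-site limit is explicit only for the baseline round.

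Under the four-site reading, control staff would discuss WE CARE evidence and context about twice in each family's follow-up. This could raise needs identification and referral in the control arm and bias the planning estimates.

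It is tempting to convert this into a loss of power for emergency department visits. The documents do not support that step. They give no leakage rate, the outcome lies several steps downstream of referral, and the plan states that this pilot will not be used to determine efficacy. The relevant harm is possible bias in the control estimates, of unknown and perhaps small size. The point is worth acting on because the remedy costs little.

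**What to change.** Reconcile Study Design, Patient Selection, Data Collection Methods, Data Management Methods, and Statistical Power and Sample Considerations so that all state the same sites and schedule.

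- **Control sites:** one baseline group, limited to current practice and context. If wanted, one further group after that site's last 12-month follow-up. No groups or study overviews in between.
- **WE CARE sites:** keep the baseline and six-monthly schedule.
- **Staff ceiling:** 60 can stand if all four sites hold at least one group. Otherwise restate it and the total of 235 to match.

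This is close to what Data Management Methods already implies. The cost is protocol wording and the loss of control-site views during follow-up; there would also be fewer meetings to run.
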